8.2.2.3 Proportion of participants moved to rescue arm or higher dose group

The percentages of subjects moved to a rescue arm or higher dose will be presented descriptively by treatment groups for the ITT and PP populations.

Note: Rescue is defined as subjects who were unable to maintain viral suppression, or experienced virologic failure, and moved to a higher dose of PRO 140.

8.2.2.4 Proportion of participants achieving viral re-suppression (HIV-1 RNA <50 copies/mL) during Treatment Phase after moving to rescue arm or higher dose group

The percentages of subjects with virologic re-suppression (as defined in [Section 7.5.8](#)) will be presented descriptively by treatment groups for the subset of the ITT and PP populations that moved to a rescue arm or higher dose group.

8.2.2.5 Time to achieving viral re-suppression (HIV-1 RNA <50 copies/mL) during Treatment Phase for subjects who moved to rescue arm or higher dose group

The number of observations, mean, standard deviation, median, and minimum and maximum values will be presented to summarize time to viral re-suppression (as defined in [Section 7.5.9](#)) by treatment groups for the subset of the ITT and PP populations that moved to a rescue arm or higher dose group.

8.2.2.6 Proportion of participants achieving viral re-suppression (HIV-1 RNA <50 copies/mL) after experiencing virologic failure (during the Treatment and Follow-up Phase)

The percentages of subjects with virologic re-suppression (as defined in [Section 7.5.8](#)) will be presented descriptively by treatment groups for the subset of the ITT and PP populations that experienced virologic failure.

8.2.2.7 Time to achieving viral re-suppression (for virologic failure subjects) after re-initiation of oral combination antiretroviral regimen during the Follow-up Phase.

The number of observations, mean, standard deviation, median, and minimum and maximum values will be presented to summarize time to viral re-suppression after re-initiation of oral combination antiretroviral regimen (as defined in [Section 7.5.10](#)) by treatment groups for the subset of the ITT and PP populations that experienced virologic failure and had re-initiation of oral combination antiviral therapy.

8.2.2.8 Proportion of participants completing 24, 48 weeks of PRO 140 treatment with HIV-1 RNA <50 copies/mL

The percentages of subjects with completing 24 and 48 weeks of PRO 140 treatment with HIV-1 RNA <50 copies/mL will be presented descriptively by treatment groups for the ITT and PP populations:

- At the Assigned dose
- Combined Assigned and Rescue dose

8.2.2.9 Mean change in CD4 cell count, at each visit within the Treatment Phase

The raw and change from baseline in CD4 cell count will be summarized for each week during the treatment phase. For change from baseline summaries, subjects with an undefined change from baseline, because of missing data, will be excluded.

8.2.2.10 To evaluate the prognostic factors of therapeutic success of PRO 140 monotherapy during the Treatment Phase

- CCR5 Receptor Occupancy: To confirm occupancy of CCR5 receptors on T-cells and monocytes or both while subjects are on PRO 140 Monotherapy and to monitor changes in CCR5 receptor occupancy status associated with changes in HIV-1 RNA levels and CD4 counts.

Data for CCR5 Receptor Occupancy will be provided from the external vendor InCell Dx. All data will be presented as a by-subject listing.

- CCR5 Genotyping Status (heterozygotes or homozygotes)

Data for CCR5 Genotyping Assay will be provided from the external vendor InCell Dx. All data will be presented as a by-subject listing.

- gp120 genotyping: To identify potential polymorphisms that may decrease PRO 140 susceptibility and may affect response to PRO 140

Data for gp120 genotype will be provided by external vendor Monogram Biosciences. All data from Monogram Biosciences will be presented as a by-subject listing.

- Baseline HIV-1 RNA Single Copy levels: To monitor changes in HIV-1 RNA single copy levels while subjects are on PRO 140 Monotherapy.

Data for HIV-1 RNA single copy assay will be provided by external vendor bioMontor Lab. All data from will be presented as a by-subject listing.

- **Immune Activation Markers:** To monitor changes in CRP, IL-6, and D-Dimer levels while subjects are on PRO 140 Monotherapy.
Data for immune activation markers will be provided by external vendor Covance. All data will be presented as by-subject listings.
- **PhenoSense® Entry Assay:** Baseline IC50, IC90 and maximal inhibition for PRO 140 and change from baseline while subjects are on PRO 140 Monotherapy
Data for PhenoSense Entry assay will be provided by external vendor Monogram Biosciences. All data will be presented as by-subject listings.

8.2.3 Exploratory outcome measures

Exploratory outcome measures will be summarized according to the variable type:

- Continuous data summaries will include number of observations, mean, standard deviation, median, and minimum and maximum values.
- Categorical data summaries will include frequency counts and percentages.

8.2.4 Additional Data listings and tabulations

8.2.4.1 Neurological Assessment

All neurological assessment findings will be listed and any abnormality will be summarized.

8.2.4.2 HIV-1 Trofile® DNA/RNA Assay

Data for HIV-1 trofile® DNA/RNA assay will be provided by external vendor Monogram Biosciences. All data will be presented as by-subject listings.

8.2.4.3 TruCount Assay (including CD4 Counts)

Data for TruCount assay will be provided by external vendor Covance. All data will be presented as by-subject listings.

8.2.4.4 Drug Resistance, Genotypic and Phenotypic data

Data for drug resistance, genotypic and phenotypic will be provided by external vendor Monogram Biosciences. All data from Monogram Biosciences will be presented as a by-subject listing.

8.2.4.5 HIV-1 Co-Receptor Tropism (exploratory assay)

Data for HIV-1 co-receptor tropism will be provided by external vendor Quest Diagnostics. All data will be presented as a by-subject listing.

8.2.4.6 Anti-Idiotypic Antibodies to PRO 140

Data for Anti-idiotypic antibodies to PRO 140 will be provided by external vendor QPS. All data will be presented as by-subject listings.

8.2.4.7 PK Concentration of PRO140

Data for PK concentration of PRO 140 will be provided by external vendor QPS. All data will be presented as by-subject listings.

8.2.4.8 Serum Concentration of ART Drugs

All serum concentration of ART drugs will be provided from the external vendor CLS. All data will be presented as a by-subject listing.

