**Table 4-1: Schedule of Assessments – Screening and Treatment Phase (T1 – T16)**

Procedure/Assessments	Visit	SV	Treatment Phase (T1 – T16)																In case of Treatment Failure VF
			T1		T2	T3	T4	T5	T6	T7	T8	T9	T10	T11	T12	T13	T14	T15	
Window Period			(Pre-Rx)	(Post-Rx)															
Informed Consent 	X																		
Eligibility Evaluation 	X																		
Pre-enrollment Eligibility		X																	
Subject Demographics	X																		
Medical History 	X	X																	
Physical Examination	X	X 		X 															
Neurological Assessment 		X																X	X
Vital Signs 	X	X	X	X	X	X	X	X	X	X	X	X	X	X	X	X	X	X	X
Body Weight & Height	X																		
ECG	X																		X
Complete Blood Count (CBC) 	X												X						X
Biochemistry 	X												X						X
Coagulation Indices	X												X						X
Serum Pregnancy Test 	X																		
Urinalysis 	X												X						X
Urine Pregnancy Test 		X																	
HBsAg	X																		
Plasma HIV-1 RNA level	X	X		X		X		X		X		X		X		X		X	X
TruCount T assay 	X	X		X		X		X		X		X		X		X		X	X
Trofile® DNA Assay	X											X							X 
Trofile® RNA Assay																			X 
HIV-1 Drug Resistance Assay 	X	X																	X
Serum concentration of ART drugs 						X				X				X					X
Randomization (via CTMS) 																			
PRO 140 Administration 																			
– Group A (350mg SC)		X		X	X	X	X	X	X	X	X	X	X	X	X	X	X	X	
– Group B (525mg SC)																			
– Group C (700mg SC)																			

Procedure/Assessments	Visit	SV	Treatment Phase (T1 – T16)																In case of Treatment Failure			
			T1 (Pre-Rx) (Post-Rx)		T2	T3	T4	T5	T6	T7	T8	T9	T10	T11	T12	T13	T14	T15	T16	VF		
Window Period			Within 6 weeks of SV			±3 days since last treatment																
Combination ART Regimen 	X		X																X			
Injection Site Reaction Assessment 				X	X	X	X	X	X	X	X	X	X	X	X	X	X	X				
Injection Site Pain Assessment (VAS) 					X	X	X	X	X	X	X	X	X	X	X	X	X	X				
PK sample for PRO 140 		X					X				X			X				X	X			
Anti-idiotypic antibodies to PRO 140 		X					X			X				X				X	X			

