**Foot Notes:**

- [1] Informed consent must be obtained prior to patient participation in any protocol-related activities that are not part of routine care.
- [2] Initial evaluation of patient eligibility will be performed by Investigator.
- [3] Medical history, past surgeries, disease history, history of substance abuse, social history, blood transfusion history, and current therapies (medications and non-medications).
- [4] Symptom-directed physical examination at clinic visits.

- [5] The neurological assessment tool is based on the three question survey used by Simioni et al. (Simioni S, 2010). Additional neurological assessment modalities may be used as per Investigator's discretion.
- [6] Vital signs (blood pressure, heart rate, respiration rate, and temperature) will be measured at clinic visit. Note: Only post-treatment vitals will be measured beyond T2.
- [7] Hemoglobin, Hematocrit (HCT), Red Blood Cells (RBC), White Blood Cells (WBC) with total and differential count, Absolute Neutrophil Count (ANC) and platelets.
- [8] Serum Biochemistry  
Hepatic function indicators: total and direct bilirubin, alkaline phosphatase, aspartate aminotransferase (AST), alanine aminotransferase (ALT), total protein, Lactate dehydrogenase (LDH)  
Renal function indicators: BUN, creatinine  
Electrolytes: sodium, potassium, chloride, calcium and bicarbonate  
Other: glucose (random), cholesterol (total)
- [9] ONLY performed on women of childbearing potential.
- [10] Urine samples will be tested for color, appearance, specific gravity, pH, protein, glucose, occult blood, ketones, leukocyte esterase, nitrite, bilirubin, urobilinogen, and microscopic examination of urine sediment.
- [11] Includes: Absolute Lymphocytes, CD3 cell count, CD4 cell count, CD8 cell count, CD3%, CD4% and CD8% Monogram Biosciences GenoSure Archive Assay will be performed at Screening and prior to PRO 140 administration at T1 visit.
- [12] Monogram Biosciences GenoSure Archive Assay performed at SV and T1; PhenoSense® GT (and PhenoSense Integrase and GeneSeq Integrase testing, if applicable), will be performed at the time of virologic failure.
- [13] To assess subject compliance in abstaining from previous ART regimen after T2 visit

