### 5.2 SUBJECT WITHDRAWAL

A subject who enters the Treatment Phase but does not complete the study, as defined in [Section 5.1](#), is considered to have prematurely withdrawn from the Study.

All subjects have the right to withdraw at any point during treatment without prejudice to future care. It will be documented whether or not each subject completed the clinical study. If for any subject, study treatment or observations were discontinued, the reason(s) will be recorded.

The Investigator can discontinue a subject at any time if it is considered medically necessary.

In addition, subjects WILL be withdrawn from the study, in consultation with the Medical Monitor and the Investigator, if any of the following are met:

- A subject is significantly non-compliant with the requirements of the protocol.
- The Investigator determines that it is in the best interest of the subject.
- Subject chooses to withdraw or is withdrawn due to an adverse event
- Recurring Grade 2 study drug injection related AE at two consecutive visits
- Occurrence of Grade 3 study drug injection related AE
- A subject becomes pregnant

**Note:** *The pregnancy will be followed to term for safety follow-up. Relevant safety information collected after the study has completed will be reported as supplemental information.*

- Discontinuation of study by Sponsor

Premature withdrawal from the study MAY occur if, in consultation with the Medical Monitor and the Investigator, any of the following are met:

- A subject is treated with a prohibited medication.

- Major protocol violation

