### 7.5.1 Excluded Medications and Therapies

1. Use of concomitant antiretroviral therapy is NOT allowed during the Treatment Phase of the study EXCEPT for one week overlap of existing retroviral regimen and PRO 140 at the beginning of the study treatment and also one week overlap at the end of the treatment in subjects who do not experience virologic failure. Subject is allowed to re-initiate antiretroviral therapy during the Treatment Phase, if virologic failure occurs or if subject meets any other criteria for discontinuation of study treatment as specified in [Section 5.2.1](#) of the protocol.
2. Use of oral or parenteral corticosteroids (> 5 mg/day) is NOT allowed during the study, with the following exceptions:
  - Use of chronic systemic corticosteroids at replacement doses (e.g., < 5mg/day prednisone) AND use of inhaled, nasal, or topical steroids are allowed.

- Use of short course of systemic corticosteroids (Medrol pack) after T2 will only be allowed with prior approval from the sponsor.
- 3. Use of radiation or cytotoxic chemotherapy, immunosuppressants and immunomodulating agents (e.g., interleukins, interferons) or agents with known anti-HIV activity (i.e., hydroxyurea, foscarnet) are NOT allowed during the study.
- 4. Use of any non-FDA approved/investigational therapy

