6.2 Per Protocol Population

The Per Protocol (PP) population is defined as the set of subjects who meet the ITT population requirements, and were not associated with a major protocol violation.

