8.2.2 Efficacy Outcome Measures

The primary analysis of efficacy outcome measures will be conducted on the ITT population. The Per Protocol (PP) population will be used as a supportive analysis.

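### Serum ART levels, drawn to check that subjects stayed off ART, are only listed, so suppression under non-permitted ART counts as PRO 140 success

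*SAP*

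**What the plan says.** Protocol Table 4-1 has a row headed "Serum concentration of ART drugs". Its footnote 13, repeated in the SAP's copy of the table, gives one purpose: "To assess subject compliance in abstaining from previous ART regimen after T2 visit". Protocol 7.5.1 states the rule being checked: "Use of concomitant antiretroviral therapy is NOT allowed during the Treatment Phase of the study EXCEPT for one week overlap". That section also permits restart after virologic failure or for another reason in Section 5.2.1.

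The only use of the results is in SAP 8.2.4.8: "All serum concentration of ART drugs will be provided from the external vendor CLS", followed by "All data will be presented as a by-subject listing".

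The endpoints are defined without them. SAP 7.5.4 defines virologic failure by two consecutive HIV-1 RNA values of at least 200 copies/mL. SAP 8.2.2.8 counts subjects who complete 24 or 48 weeks of PRO 140 with HIV-1 RNA below 50 copies/mL. On populations, SAP 8.2.2 says "The primary analysis of efficacy outcome measures will be conducted on the ITT population", and SAP 6.1 puts every enrolled or randomized subject with at least one dose into ITT. SAP 6.2 limits PP to ITT subjects who "were not associated with a major protocol violation". Neither document says what makes a violation major.

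**The concern.** The question is whether PRO 140 alone keeps already suppressed patients suppressed. Continued or resumed ART gives the same viral load result as drug success. The trial schedules a measurement that can tell the two apart, but the analysis plan does not use it. Non-permitted ART use can only make failure look rarer and suppression more common. If use differs between dose groups, it can also create an apparent dose difference. Because the trial is open label and has no rule fixed in advance, any decision about individual positive results would be made with outcomes and doses known.

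**Working it through.** **Does any rule act on a positive level?**

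- *Positive result:* no threshold is given in either document.
- *VF and the week 24/48 proportion:* these rest on HIV-1 RNA, and for the latter also on completing PRO 140. ART status does not enter.
- *ITT:* there is no condition on ART use.
- *PP:* exclusion depends on an undefined term.
- *Withdrawal:* Protocol 5.2 lists "A subject is treated with a prohibited medication" as a reason for which withdrawal may occur. A subject withdrawn on that ground is censored at early termination for time to VF (SAP 7.5.5), with no imputation (SAP 7.3). That subject is never a failure, although one withdrawn early would not complete 24 or 48 weeks.
- *Deviations and ART tables:* SAP 8.1.2 summarizes and lists deviations. SAP 8.1.5 covers ART recorded in the eCRF, where undisclosed use would not appear.

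No rule changes how an endpoint is counted.

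**Size, for illustration only.** The documents give no figure to reproduce. Let p be the VF proportion on true monotherapy and c the share covertly on ART, and assume that share does not fail.

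- Observed VF = p × (1 − c), so VF is understated by p × c.
- Upper p: in the earlier 12-week 350 mg study (Protocol 1.4.2.7), 23 of 43 completed without failure, so 20/43 = 46.5% did not. That study used a 400 copies/mL definition, and the 20 may include dropouts without failure. It is an anchor, not a forecast.
- Lower p (20%) and c (2% to 10%) are assumptions with no source in the documents.

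| p | c = 2% | c = 5% | c = 10% |
|---|---|---|---|
| 20% | 0.4 | 1.0 | 2.0 |
| 35% | 0.7 | 1.75 | 3.5 |
| 46.5% | 0.9 | 2.3 | 4.7 |

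Entries are percentage points. If covert users sometimes fail, the understatement is smaller.

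*Between groups:* with a true VF of 35% at both 525 mg and 700 mg, and covert use 10 points higher in one, the spurious difference is 0.35 × 0.10 = 3.5 points.

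**Coverage of the samples.** Read against the HIV-1 RNA row, the marks in Table 4-1 fall at T4, T8, T12 and VF. The columns come from extracted text and should be confirmed in the PDF. Table 4-2 (T17 to T48) has no such row. Of the 44 visits from T3 to T46, 34 (T13 to T46) follow the last routine sample: 34/44 = 77%.

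**The case against.** *The PP analysis may already deal with this.* Non-permitted ART breaches Protocol 7.5.1, must be recorded as a deviation (Protocol 11.4) and could be judged major. This stands as a possibility. A reader might infer the opposite, that such subjects must stay in PP because Protocol 5.2 lists prohibited medication apart from major violation. The text does not support that: those bullets are optional reasons for withdrawal, not violation classes. What the documents support is that the matter is undecided. PP is in any case only supportive.

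*The assay may be a remnant.* The protocol contents list a section on serum ART levels with a bookmark error. In the body, 7.10.13 is now the biomarker section, and the visit lists in 4.2.2, 4.2.3 and 4.3 omit the sample. This stands, and collection must be confirmed. But the row and footnote remain in both documents, and SAP 8.2.4.8 names a vendor.

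*The samples cannot carry the remedy.* This stands in part. A covert user who stays suppressed never reaches a VF sample, so use after T12 is invisible. The remedy uses the evidence available and does not rule out later use.

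*The effect is small beside sampling error.* For 100 subjects at 700 mg, the 95% half-width is 1.96 × √(p(1 − p)/100): 7.8 points at 20% and 9.8 at 46.5%. The illustrated bias is smaller. But it runs in one direction and does not shrink as subjects are added.

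*There is no ART control arm.* A reader might think such an arm would expose the problem. It would not show covert ART use within a PRO 140 group, so its absence is no part of this point.

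**Conclusion.** The point holds for the primary ITT analysis: as written, suppression under non-permitted ART is counted as PRO 140 success, and the one measurement scheduled to detect it has no analytic role. For PP, the outcome depends on an undefined term.

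The direction is clear, towards a more favourable result, but the size is not known. The range of 0.4 to 4.7 points rests on an assumed VF of 20% to 46.5%, an assumed covert share of 2% to 10%, and no failures among covert users. A reader might infer that hidden ART use did occur, or occurred at about these rates. The documents do not show that. Protocol 1.4.2.8 reports one subject, among 16 eligible in the extension study, withdrawn for restarting ART. That case was known, so it shows that restart happens, not how often it is concealed.

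The SAP should be changed before database lock. The primary analysis need not change.

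**What to change.** 1. **Confirm collection.** State for which subjects and visits serum ART was measured and which drugs the assay covers, and reconcile Table 4-1 with the protocol body.
2. **SAP 6.2.** Class a quantifiable level of a prior-regimen ART drug after the initial overlap as a major violation that excludes the subject from PP. Set a washout allowance for each drug before lock; the documents give no figures for this. Exempt samples taken after any restart the protocol permits: after VF, at the planned Week-47 restart, or for another Section 5.2.1 reason.
3. **SAP 8.2.2.** Add two ITT sensitivity analyses for subjects with a non-exempt positive level. One counts them as non-successes at the assigned dose from the first positive sample; the other censors them there. Present both beside the unchanged primary result. The first is deliberately severe: if every covert user were detected, it would give p(1 − c) + c, which exceeds p by c(1 − p). At p = 20% and c = 10% that is 8 points. The second assumes that ART use is unrelated to the risk of failure.
4. **SAP 8.2.4.8.** Tabulate subjects tested and subjects positive, by dose group and visit.
5. **State the limit.** If the schedule is as read here, use after T12 in subjects who stay suppressed is not detected.

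The cost is SAP wording, one table and two sensitivity rows. No new samples are needed and patient management is unchanged. The success figures in the added analyses may be slightly less favourable.

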8.2.4.9 Notification and Outcome Pregnancy

All the results for Notification and Outcome Pregnancy will be presented as a by-subject listing.

8.2.4.10 Weight

Weight data will be summarized and presented as by-subject listing.

8.2.4.11 Height

Height data will be summarized and presented as by-subject listing.

8.2.4.12 Urine drug test

All available urine drug test data will be presented as by-subject listing.

8.2.4.13 Pregnancy test

All available pregnancy data will be presented as by-subject listing.

9. APPENDIX – PLANNED TLG

9.1 Planned by-subject listings

DISPOSITION/WITHDRAWALS (LISTINGS 16.2.1.X)

ELIGIBILITY AND PROTOCOL DEVIATIONS (LISTINGS 16.2.2.X)

EXCLUDED SUBJECTS (LISTINGS 16.2.3.X)

DEMOGRAPHICS, POPULATION, AND BASELINE CHARACTERISTICS
(LISTINGS 16.2.4.X)

TREATMENT ADMINISTRATION LISTINGS (LISTINGS 16.2.5.X)

EFFICACY RESPONSE DATA (LISTINGS 16.2.6.X)

ADVERSE EVENT DATA (LISTINGS 16.2.7.X)

SAFETY DATA (LISTINGS 16.2.8.X)

9.2 Planned Summary Tables

POPULATION DISPOSITION AND PROTOCOL DEVIATIONS

POPULATION DEMOGRAPHICS AND BASELINE CHARACTERISTICS

CONCOMITANT MEDICATION USAGE

EFFICACY SUMMARIES

SAFETY SUMMARIES

ADVERSE EVENT SUMMARIES

SERIOUS ADVERSE EVENTS

LABORATORY

VITAL SIGNS

PE

ECG

TOLERABILITY

NEUROLOGICAL ASSESSMENT

OTHER SAFETY

